7.4.1 Primary analysis

The primary analysis will be based on the TS (according to randomised treatment), using all available data from baseline (excluded) up to Week 52, including visits done after premature treatment discontinuation, EOT visits and follow-up visits done before Week 52 (i.e. including all measurements after first drug intake and before or on day 373). Patients will be analysed based on the fibrotic pattern data entered in the eCRF, which may not necessarily coincide with data used for randomisation. Details on sensitivity analyses can be found in [Section 7.4.2](#).

The primary analysis uses a restricted maximum likelihood (REML) based approach with a random slope and intercept model. The analysis will include the fixed, categorical effects of treatment, HRCT pattern, fixed continuous effects of time and baseline FVC (ml) as well as the treatment-by-time and baseline-by-time interactions. Random effects will be included for patient response for both time and intercept.

The statistical model can be written as follows:

$$y_{ijkm} = (\alpha + a_i + \vartheta_m + \beta_0 S_i + \tau_k) + (\gamma + g_i + \beta_s S_i + \varphi_k) t_{ij} + e_{ij}$$

$$(a_i, g_i) \sim N_2 (\mathbf{0}, \Sigma)$$

$$e_{ij} \stackrel{iid}{\sim} N (0, \sigma^2)$$

The components of the model are as follows:

y_{ijkm}	=	response variable for patient i with HRCT pattern m at visit j receiving treatment k
α	=	mean patient intercept
a_i	=	random intercept effect for patient i, $i=1,2,\dots$
ϑ_m	=	intercept coefficient of HRCT pattern (“other HRCT fibrotic patterns” as the class reference)
β_0	=	intercept coefficient of baseline FVC (ml)
S_i	=	baseline FVC (ml) measurement for patient i
τ_k	=	intercept coefficient of the effect of treatment k, $k=1,2$
γ	=	mean patient slope
g_i	=	random slope effect for patient i
β_s	=	slope coefficient of baseline FVC (ml)

φ_k = slope coefficient of the effect of treatment k
 t_{ij} = time of measurement j for patient i, $j = 1, 2, \dots, J$
 e_{ij} = the random error associated with the j^{th} visit of patient i. Measurement errors are independent and normally distributed with mean 0 and variance σ^2 , and uncorrelated with a_i and g_i .
 Σ = a 2x2 unstructured covariance matrix

For the co-primary evaluation of FVC (in ml over 52 weeks) in patients with “HRCT with UIP-like fibrotic pattern only”, the following model will be utilised:

$$\begin{aligned}

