7.4.2 Sensitivity analyses

Sensitivity analyses for FVC (in ml over 52 weeks) using different assumptions will be conducted to investigate the potential effect of data handling, missing data and the analysis model (e.g. assumption of linearity) on the results of the main analysis. In addition, it will be evaluated, whether potential discrepancies between IRT and eCRF of HRCT pattern have an impact if more than 3% of the randomised patients show such discordance.

For all sensitivity analyses to data handling assumptions the estimate, two-sided 95% Confidence Interval and p-value of the treatment effect will be represented on the same Forest plot. Tables presenting the results of the sensitivity analyses will be created in addition to graphical representations, and included in the CTR Appendix.

Interpretation of sensitivity analyses:

Separate forest-plots will be produced for each of the co-primary evaluations in Section 15 of the CTR. In case the results of some of the sensitivity analyses are inconsistent with those of the primary analysis (i.e. the treatment effect estimate of a sensitivity analysis lies outside the confidence interval of the treatment effect of the primary analysis), clinical input will be needed to assess the clinical relevance of the difference.

Sensitivity analyses described in the CTP will be discussed in this section, additional sensitivity analyses in [Section 9.12](#).

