Sensitivity 3 ^[2]	based upon the slope (SE) estimates in Placebo patients from the primary analysis model (MMRM), i.e. in patients from pattern 1 or 2: multiple imputation of missing week 52 data in all patients regardless of treatment group	rate of decline in all patients with missing week 52 data is similar to rate of decline estimated in all Placebo patients (e.g. treatment effect does not persist after trial drug discontinuation)	multiple imputation of missing 52 week data due to death based on the same slope (SE) estimates in all Placebo patients (i.e. in patients from pattern 1 or 2), but truncated ^[3] to force the slope in patients who died to be more severe than in those who survived	Assuming that deaths observed in the trial will likely be related to worsening of the underlying disease, it seems reasonable to assume that the unobserved FVC values should on average be lower than those in patients who did not die prior to week 52

- [1] Sensitivity analyses 1 and 2 will only be performed if the number of patients in pattern 2 is greater than 10 (from both Nintedanib and Placebo group for sensitivity analysis 1 and from placebo group for sensitivity analysis 2)
- [2] Patients falling into pattern 2 are used as the basis for multiple imputations but since the number of patients in that pattern may be small, a third sensitivity analysis will be performed to confirm the robustness of the primary analysis results.
- [3] If β represents the true slope with $f(\beta) \sim N(\hat{\beta}, \hat{\sigma}^2)$ where $\hat{\beta}$ and $\hat{\sigma}$ are the placebo slope and SE estimates from either patients in pattern 2 or all placebo patients, then sampling for patients who died prior to 52 weeks is restricted to the interval $(-\infty, \hat{\beta}]$ of the truncated distribution $f(\beta)/2$. In this way, it is guaranteed that, on average, the imputed FVC slope for patients who died is steeper than the average slope in patients who survived to week 52.

In addition to the patterns defined in the scope of the multiple imputation, the number (and percentage) of patients in each possible pattern of FVC data will be explored. Graphs showing FVC data over time in each pattern of monotonic missing data will also be provided. These outputs will be shown in the CTR Appendix.

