9.5 PROGRAMMING CODE FOR INFERENTIAL ANALYSIS

9.5.1 Primary endpoint model

The key code is given below. Time is defined as duration since first trial drug intake divided by 365.25. Visit is the visit number. For the co-primary population, please remove HRCT as variable from the model.

```

ODS OUTPUT estimates=estimateout;
PROC MIXED data=FVC cl method=reml order= formatted covtest;
  CLASS patient treatment hrct;
  MODEL endpoint= treatment treatment*time hrct fvcbaseline fvcbaseline*time /solution CL
    ddfm=KR;
  RANDOM intercept time/ type=un subject=patient;
  ESTIMATE 'Nintedanib' fvcbaseline*time meanbase treatment*time 0 1 / e CL;
  ESTIMATE 'Placebo' fvcbaseline*time meanbase treatment*time 1 0 / e CL;
  ESTIMATE 'Nintedanib 150mg bid – Placebo' treatment*time -1 1 / e CL;
RUN;
ODS OUTPUT CLOSE;

```

9.5.2 Primary endpoint subgroup analysis model:

Example subgroup used: Gender (Male / Female).

```

ODS OUTPUT estimates=estimatesout Contrasts=contrastsout ;
PROC MIXED data=FVC cl method=reml order= formatted covtest;
  CLASS patient treatment hrct subgroup;
  MODEL endpoint= treatment*subgroup treatment*subgroup*time
    hrct fvcbaseline fvcbaseline*time
    /solution CL ddfm=KR;
  RANDOM intercept time/ type=un subject=patient;
  ESTIMATE 'Nintedanib - Female' fvcbaseline*time meanbase treatment * subgroup *time 0 0 1 0
    / cl e;
  ESTIMATE 'Placebo - Female' fvcbaseline*time meanbase treatment * subgroup *time 1 0 0 0
    / cl e;
  ESTIMATE 'Nintedanib - Male' fvcbaseline*time meanbase treatment * subgroup *time 0 0 0 1 /
    cl e;
  ESTIMATE 'Placebo - Male' fvcbaseline*time meanbase treatment * subgroup *time 0 1 0 0
    / cl e;
  ESTIMATE 'Nintedanib – Placebo Female' subgroup * treatment *time
    -1 0 1 0 / e CL;
  ESTIMATE 'Nintedanib – Placebo Male' subgroup * treatment *time
    0 -1 0 1 / e CL;
  CONTRAST 'F-test of heterogeneity at 52 weeks'
    subgroup * treatment *time -1 1 1 -1 / e;
RUN;
ODS OUTPUT CLOSE ;

```

9.5.3 Implementation of multiple imputation:

The following steps provide a guidance of how missing FVC data at week 52 will be implemented in patients of pattern 3 and 4 using multiple imputation. Refer to [Table 7.4.2.1.2: 1](#) for the description of patterns and the different sensitivity analyses regarding handling of missing data.

1. Run the MMRM of the primary analysis (either including patients of pattern 2 only for sensitivity analyses 1 and 2 or on all patients for sensitivity analysis 3) to get the slope

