
estimates (SE) by treatment group. Let $\hat{\beta}_D$ and $\hat{\sigma}_D$ denote the slope (SE) estimates in Nintedanib 150 mg and $\hat{\beta}_P$ and $\hat{\sigma}_P$ the slope (SE) estimates in placebo.

2. Let β_D and β_P represent the true slopes in drug and placebo respectively with $f(\beta_D) \sim N(\hat{\beta}_D, \hat{\sigma}^2_D)$ and with $f(\beta_P) \sim N(\hat{\beta}_P, \hat{\sigma}^2_P)$, using the slope (SE) estimates obtained in step 1.
3. Imputation of missing week 52 data in patients of pattern 3:

Multiple impute missing values (1000 imputations per patient). To do so, draw random slopes from the distributions defined in step 2. Considering that the withdrawal of a patient leading to missing data can occur at any time during the study, the timepoint of the last available FVC value has to be taken into account to impute the missing FVC value at 52 weeks.

$$\text{FVC week 52 imputed}_{ij} = \text{last FVC value available}_i + \hat{\beta}_{ij}(\text{time between date of last FVC value available}_i \text{ and planned 52 week timepoint [days]})$$

where i denotes the indicator of the i^{th} patient, j the indicator of the j^{th} imputation and $\hat{\beta}_{ij}$ denotes a random slope sampled from the distribution mentioned in step 3a for the i^{th} patient in the j^{th} imputation. Depending on the sensitivity analysis, use either random slopes drawn from $f(\beta_D)$ for patients randomised to Nintedanib 150 mg in sensitivity analysis 1 or $f(\beta_P)$ for all patients in sensitivity analyses 2 and 3.

4. Imputation of missing week 52 data in patients of pattern 4:

Multiple impute missing values (1000 imputations per patient). To do so, draw random slopes from the truncated distribution $f(\beta_P)/2$ restricted to the interval $(-\infty, \hat{\beta}_P]$ defined in step 2.

See step 3 for further details on how to use these slopes to impute the missing values at week 52.

5. Run the MMRM of the primary analysis on each imputed dataset, using a "by _IMPUTATION_" statement.
6. Combine the estimates obtained in step 5 using PROC MIANALYZE.

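### SAP 9.5.3 uses the standard error of a group slope as the spread between patients, so Sensitivity analysis 1 reports too small an error; it also mixes years with days and contradicts itself on the Sensitivity 2 reference group

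*SAP*

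**What the plan says.** SAP 7.4.2.1.2 defines three multiple-imputation analyses for patients without a week-52 FVC: those alive (pattern 3) and those who died (pattern 4). It says the imputation model will resemble the primary model. SAP 9.5.3 gives the steps.

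- **Steps 1–2.** Fit the primary model in the reference patients, take each arm's slope and standard error (SE), and give the arm's true slope the distribution N(estimate, SE²).
- **Step 3 (pattern 3).** "To do so, draw random slopes from the distributions defined in step 2". The draw is indexed by patient and by imputation, and is described as "sampled from the distribution mentioned in step 3a"; there is no step 3a. Imputed FVC is the last FVC plus the drawn slope times the interval from the last FVC "and planned 52 week timepoint [days", where the bracket gives the unit.
- **Step 4 (pattern 4).** Draw from the same SE-based placebo distribution, truncated at its mean. Footnote 3 of Table 7.4.2.1.2: 1 says that on average "the imputed FVC slope for patients who died is steeper than the average slope in patients who survived to week 52".

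Other relevant text:

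- SAP 7.4.1: "Random effects will be included for patient response for both time and intercept", with a residual variance as well.
- SAP 9.5.1: "Time is defined as duration since first trial drug intake divided by 365.25", so slopes are in mL/year.
- Footnote 1 of the same table: "Sensitivity analyses 1 and 2 will only be performed if the number of patients in pattern 2 is greater than 10".
- SAP 7.4.2: for these analyses "the estimate, two-sided 95% Confidence Interval and p-value of the treatment effect will be represented on the same Forest plot".

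**The concern.** An SE describes how well one group mean is known. It is not how far individual patients differ from that mean, and its error is shared by everyone imputed from it. Independent draws per patient cancel that shared error, and leaving out patient slope variance and residual error makes the imputed values too regular. Rubin's rules then see almost no between-imputation variance.

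Sensitivity 1 suffers most, because each arm is imputed from its own pattern 2 slope, which may rest on as few as 11 patients. In Sensitivities 2 and 3 both arms use the same placebo slope, so its error largely cancels from the treatment difference.

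At stake is the reading of the forest plot. An interval that narrows as data go missing would be taken as evidence of robustness to missing data. Separately, the unit mismatch gives impossible FVC values if followed literally, and the reference-group conflict lets two programmers produce two different analyses from one plan.

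**Working it through.** **Inputs from the documents.** 300 per arm, overall effect 92 mL/year, SD 337 mL/year (protocol 7.7); pattern 2 minimum of 11 (footnote 1); IPF mortality of 7.8% on placebo and 5.5% on nintedanib (protocol 1.2). Section 9.5.3 states no numerical result to reproduce. Re-coding protocol Appendix 10.6 returned its stated figures: alpha 4.35%, Scenario 1 power 90.2%, 90.3% and 92.6%.

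**Assumed, because the documents do not give them.** The share of patients in pattern 3, the size of pattern 2, and the variance components.

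**1a. Why the variance disappears.** With SD 337 and 11 pattern 2 patients, SE = 337/√11 = 101.6 mL/year. Suppose 20% of an arm (60 patients) is in pattern 3. A shared draw moves their average slope with SD 101.6 across imputations. Independent draws move it with SD 101.6/√60 = 13.1. With 30 pattern 2 patients the figures are 61.5 and 61.5/√60 = 7.9.

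**1b. Simulated rejection rate of Sensitivity 1.** Null effect, no deaths, two-sided 5% level.

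- *Simulation A:* slope SD 280, residual SD 100, intercept SD 150; fixed effects reduced to treatment, time and their interaction; 3,200 trials per setting (Monte Carlo error 0.4–0.7 points); 3 imputations as written, 8 corrected.
- *Simulation B:* separately coded; slope SD 280, residual SD 110; 2,000 trials (error about 0.5 points at a 5% rate); 30 imputations.

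| Simulation | Pattern 2 per arm | Pattern 3 share | As written | Corrected |
|---|---|---|---|---|
| A | 30 | 8 / 12 / 20% | 6.8 / 7.9 / 11.4% | 4.7–5.6% (all six settings) |
| A | 11 | 8 / 12 / 20% | 7.3 / 10.3 / 16.4% | as above |
| B | 30 | 5 / 10 / 20% | 5.5 / 6.5 / 10.3% | 4.7 / 5.1 / 5.7% |
| B | 11 | 5 / 10 / 20% | 5.8 / 7.5 / 13.6% | 5.0 / 5.1 / 5.4% |

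A third run (residual SD 110, 2,500 trials) gave 6.2% (30 patients, 8%), 7.4% (30, 12%) and 9.0% (11, 12%), against 5.1–5.4% corrected.

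**1c. Standard errors.** In A with 30 pattern 2 patients, at 8 / 12 / 20% missing:

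- reported SE of Sensitivity 1: 24.0 / 23.7 / 23.0
- true SD of its estimate: 25.7 / 26.2 / 28.7
- primary-analysis SE: 25.4 / 25.8 / 26.7

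The reported error falls while the true error rises. The between-imputation SD in A was 0.9–2.3 mL/year as written and 6.9–19.9 corrected. Sensitivities 2 and 3 as written rejected in 4.3–5.5% (A) and 4.5–5.3% (B) of trials.

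**1d. Truncation for deaths.** A normal distribution cut at its mean shifts by √(2/π) = 0.80 times its spread. The ranges use SD 302 (simulation A's components) to 337 (planning).

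| Spread used | Shift, mL/year |
|---|---|
| SE, 300 placebo patients | 14–16 |
| SE, 40 pattern 2 patients | 38–43 |
| SE, 11 pattern 2 patients | 73–81 |
| Patient-level slope SD 280 | 0.80 × 280 = 223 |

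The SE-based shift satisfies footnote 3. It does not match the stated Sensitivity 2 assumption that patients who died decline like the steepest pattern 2 placebo patients.

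With the IPF mortality rates, a true effect of 92, 8% in pattern 3 and 30 pattern 2 patients per arm (600 trials, 5 corrected imputations), correction moves the estimates from 89.2 to 92.4, 84.1 to 86.9 and 83.7 to 87.2 mL/year for Sensitivities 1 to 3.

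**2. Units.** For an illustrative −190 mL/year with 182 days missing, the formula as written gives −190 × 182 = −34,580 mL. The intended change is −190 × 182/365.25 = −95 mL.

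**3. Reference group for deaths in Sensitivity 2.**

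| Place | Placebo reference |
|---|---|
| SAP Table 7.4.2.1.2: 1, handling cell | patterns 1 or 2 |
| Same row, assumption cell | pattern 2 |
| SAP 9.5.3, step 1 | pattern 2 only |
| Protocol Table 7.5.1: 1 | subset 2, printed in the Sensitivity 1 row; the Sensitivity 2 cell is blank and appears merged with it |

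The choice moves the estimate by about 1 mL/year, even if pattern 2 slopes are 100 mL/year steeper.

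**The case against.** **Not a trial error rate.** Success rests on the primary analysis under Hochberg. The SAP judges consistency by whether a sensitivity estimate falls inside the primary confidence interval, it ranks the on-treatment analysis first, and it adds a tipping-point analysis. All of this stands, and it limits the consequence. It does not make a published interval and p-value correct.

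**Conclusions would hardly change.** In the scenario with deaths, Sensitivity 1 has z = 89.2/23.5 = 3.8 as written and 92.4/26.3 = 3.5 corrected. The corrected death handling also moves the estimates towards nintedanib. This stands at the planned effect; a weaker effect would leave less room.

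**The large figures are corner cases.** Eleven in pattern 2 with 20% missing means 60 of 71 such patients per arm were lost by week 52, despite a design that follows patients after discontinuation. Thirty with 20% means 90 of 300. The protocol's IPF figures for adverse-event discontinuation are 19% and 13%. The simulations also differ in that corner (16.4% and 13.6%), and at 5% missing the excess is under one point. The size is therefore uncertain, but the direction is the same in every setting.

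**The simulations simplify.** Simulation A omits HRCT pattern and baseline FVC, and the imputation counts are far below the SAP's 1000. This is fair; the three runs still agree on the mechanism and on the repair.

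**The remedy is one choice among several.** Adding a residual to an observed last value, which already contains one, is not an exact draw from the model. Patient-level truncation goes beyond the protocol's requirement of similar or worse decline. Both points stand, and Sensitivities 2 and 3 become mildly conservative.

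**The unit and cross-reference errors are editorial.** A programmer would probably catch the units. The reference group cannot be resolved without choosing between conflicting instructions.

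**Conclusion.** The point holds in all three parts and should be fixed. As written, Sensitivity 1 reports an SE below that of the primary analysis, and the SE shrinks as more week-52 data are missing. Its rejection rate under no effect is about 5.5–6% with 5% missing, 6–10% with 8–12% missing and 10–16% with 20% missing. These figures assume slope SD 280, residual SD 100–110 and 11–30 pattern 2 patients per arm; the documents give neither the missingness rate nor the variance components.

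Sensitivities 2 and 3 show no inflation, point estimates move by only 3–4 mL/year, and the confirmatory result is not affected. What is wrong is the precision shown for one analysis on the forest plot, plus text that cannot be programmed as it stands.

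**What to change.** Rewrite steps 2–4 of SAP 9.5.3 before the first database lock:

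1. In each imputation, draw each reference mean slope once from N(estimate, SE²).
2. Draw each patient's slope from a normal distribution with that mean and the model's estimated random-slope variance. Use the fitted components, not the planning SD of 337.
3. Set imputed FVC = last FVC + slope × (remaining days / 365.25) + a residual drawn with the model's residual variance.
4. For pattern 4, truncate the patient-level distribution at the placebo mean. The renormalised density is twice f on that half-line, not f/2.
5. Set the Sensitivity 2, pattern 4 handling cell to placebo pattern 2, in line with its assumption cell and step 1.
6. Replace the reference to step 3a with step 2.

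The cost is SAP wording and a few lines of code. Intervals widen: in the scenario with deaths, the Sensitivity 1 SE rises from 23.5 to 26.3. In Sensitivities 2 and 3 the corrected SE (about 25.7) slightly exceeds the repeated-sampling SD (about 24.4).

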9.6 SPECIAL ADAM COMPOSITION INSTRUCTIONS

9.6.1 ADEX

The analysis of exposure will be based on the drug administration as planned and documented in the eCRF, i.e. the derivation of ADEX will be mainly based on EC. In case an administration entry for a visit is missing, it will be checked whether the patient was treated using the compliance data in XA; if this is the case, the missing drug administration data will

be replaced using the drug dispensation data in DA for the same visit if available. Treatment start will be the first treatment date/time as in ADEX.

9.7 LIST OF BI CUSTOMISED DRUG GROUPINGS OF INTEREST

Drug groupings of interest for this trial are shown in the following Table.

Table 9.7: 1 Concomitant Therapy groupings

CT grouping name	Type of grouping
Biologic DMARDs	SDG
Non-biologic DMARDs	SDG
Antithrombotic drugs	SDG

The table below shows the overview of medications that are considered to fall into the respective category of Disease-Modifying Anti-Rheumatic Drugs (DMARDs) with known hepatotoxic or gastrointestinal effects. Please note that an individual substance can occur in both categories.

Table 9.7: 2 DMARDs with known hepatotoxic or gastrointestinal effects

DMARDs with known hepatotoxic effects		DMARDs with known gastrointestinal effects	
WHO-DD decode	WHO-DD code	WHO-DD decode	WHO-DD code
LEFLUNOMIDE	01414801001	ABATACEPT	05514401001
METHOTREXATE	00113801001	LEFLUNOMIDE	01414801001
METHOTREXATE SODIUM	00113802001	METHOTREXATE	00113801001
TOCILIZUMAB	01759101001	METHOTREXATE SODIUM	00113802001
TOFACITINIB	07918601001	SULFASALAZINE	00001601001
TOFACITINIB CITRATE	07918602001	TOFACITINIB	07918601001
		TOFACITINIB CITRATE	07918602001

9.8 SPECIFICATION OF RESTRICTED AND FORBIDDEN CONCOMITANT THERAPIES

Categorisations and detailed information on WHO-DD code can be found in the following Table.

Table 9.8: 1 Prohibited or restricted concomitant therapies

Type of medication	Category of drugs	WHO-DD code
Prohibited	Full dose therapeutic anticoagulation or high dose antiplatelet therapy	0000000126
Prohibited	Pirfenidone	06225101001
Prohibited	Nintedanib	08403301001, 08403302001
Restricted	Oral corticosteroids (OCS)	0000000010
Restricted	Immunomodulatory medications for ILD	00001501001, 00001502001, 00021101001, 00021102001, 00549701001, 01275102001, 01275104001, 01402501001 01219901001, 01219902001

9.9 LIST OF POTENTIAL TERMS FOR HEPATIC INJURY DERIVATION

The table below shows the list of potentially relevant MedDRA preferred terms to support the derivation of a potential hepatic injury.

Table 9.9: 1 List of potentially relevant MedDRA preferred terms

Symptom	MedDRA
Vomiting	PT Vomiting
Fatigue	PT Fatigue
Nausea	PT Nausea
Right upper abdominal quadrant pain or tenderness	HLT “Gastrointestinal and abdominal pains (excl oral and throat)”
Fever	PT Pyrexia
Rash	BIcMQ skin rash (narrow)

